#### 1. INTRODUCTION

The purpose of this statistical analysis plan (SAP) is to provide details of the analysis for protocol ANK-700-01. The statistical methods described herein are based on the analyses proposed in the Final Protocol V4 dated 06 June 2022 and the associated CRF (Case Report Form) dated 12Sept2022 This SAP supersedes the statistical considerations identified in the protocol. Any analyses that are substantially different will be identified in Section 10. This document is written with consideration of the recommendations outlined in the International Conference on Harmonization (ICH) E9 Guideline (Guidance for Industry: Statistical Principles for Clinical Trials) and on the ICH E3 Guideline (Guidance for Industry: Structure and Content of Clinical Study Reports).

The SAP will be developed and finalized prior to database lock and unblinding of the clinical database. The analyses identified in this SAP were developed for regulatory submissions and/or future manuscripts. Additional exploratory analyses, not necessarily identified in this SAP, may be performed to support the clinical development program.

#### 1.1 Background

Multiple sclerosis (MS) is a chronic and often disabling autoimmune disease of the central nervous system (CNS) characterized by loss of motor, sensory, cognitive, and autonomic function. MS is associated with the human leukocyte antigen (HLA) DRB1\*15:01 allele, and patients with a homozygous genotype have an increased risk, both for susceptibility of inheriting the disease and in the severity of their disease.

ANK-700 is	composed of a CNS-derived synthetic
peptide, ANK-07,	to enable liver-specific
distribution and immune tolerance induction. T	he mechanism of action of ANK-700

harnesses natural tolerogenic pathways in the liver to re-educate pathogenic immune cells to become tolerant towards MS antigens. ANK-700 specifically targets the immune cells that drive MS and leaves the otherwise healthy components of the immune system intact to perform their natural, protective functions. Surrogates of ANK-700 have demonstrated efficacy in mouse models of MS.

#### 2. GENERAL STUDY DESIGN AND PLAN

## 2.1 Study Objectives

#### 2.1.1 Primary

• Assess the safety and tolerability of escalating doses of ANK-700 in patients with RRMS (Relapsing Remitting Multiple Sclerosis)

## 2.1.2 Secondary

• Evaluate the Pharmacokinetic (PK) of escalating doses of ANK-700 in patients with RRMS

## 2.2 Study Population

The study population includes adults (18 to 60 years inclusive, at screening) with RRMS based on revised McDonald criteria (2017) with an Expanded Disability Status Scale (EDSS) score  $\leq$  6.5. Patients must be neurologically stable with no evidence of relapse within the 28 days before signing the informed consent form. These criteria have been implemented to evaluate the safety and tolerability of ANK-700 in a diverse RRMS population which has an appropriate risk/benefit profile based upon the severity of their disease. The population selected for this study (ie, those with relatively well controlled and neurologically stable RRMS) is appropriate for the FIH study, as highly active disease may obscure the assessment of safety and tolerability of ANK-700 and may require active management during the study period.

[figure not shown]
Patients receiving a stable dose of a fumarate drug (ie, dimethyl fumarate, diroximel fumarate) for  $\geq 6$  months will be allowed to remain on stable doses of fumarates (dimethyl fumarate or diroximel fumarate) during the study because fumarate drugs do not interfere with the mechanism of action of ANK-700. Patients using any other disease modifying therapies (DMT) to treat MS will be excluded.

#### 2.3 Study Design

Study ANK-700-01 is a Phase 1, FIH (First in Human) study designed to evaluate the initial safety, tolerability, and activity of ANK-700 in patients with RRMS.

A graphic overview of the 2 parts (Part A: Single Ascending Dose (SAD) and Part B: Multiple Ascending Doses (MAD)) is presented below.

Figure 1: Overview Study ANK-700-01

**Single Ascending Dose (SAD) (Part A):** 3 patients will be dosed IV with ANK-700 in each cohort. Initiation of the next dose cohort will commence once all patients in a cohort reach D15 and upon acceptable safety review and recommendation by SMC and approval by the Sponsor.

Multiple Ascending Dose (MAD) (Part B): the first MAD cohort (Cohort 4) will be initiated only after acceptable safety review of SAD Cohort 2, recommendation by the SMC, and approval by the Sponsor. Patients are randomized 2:1 to ANK-700 or PBO. Initiation of Cohort 5 will commence once all patients in Cohort 4 reach D22 and upon acceptable safety review of Cohorts 1 to 4, recommendation by the SMC, and approval by the Sponsor.

**Abbreviations**: D = day; IV = intravenously; MAD = multiple ascending dose; PBO = placebo; SAD = single ascending dose; SMC = Safety Monitoring Committee.

#### 2.3.1 PART A: SAD (Single Ascending Dose)

The SAD phase will include up to 3 cohorts with 3 patients each. Patients within each dose cohort will receive 1 dose of ANK-700 IV and will be monitored for up to 6 months. All patients in Part A will be dosed  $\geq$  14 days apart to monitor for acute and subacute reactions; this length of time is supported by nonclinical exposure data that suggest ANK-700 will have cleared > 5 half-lives and nonclinical animal model data demonstrating that the tolerance induction mechanism can develop, and immunologically active peptide is cleared within 1 week from dosing.

Doses evaluated in Part A include 0.3 mg/kg (Cohort 1), 1.0 mg/kg (Cohort 2), and 3.0 mg/kg (Cohort 3). After all patients within a given dose cohort have been followed for  $\geq$  14 days post dose, a safety review will be performed by the SMC to review all adverse events (AEs) and available clinical laboratory and PK data. Initiation of the next dose level will commence upon recommendation by the SMC and approval by the Sponsor.

Part A will employ a 3+3 design to evaluate single ascending doses of ANK-700. At any dose level, if none of the first 3 patients dosed experience a dose-limiting toxicity (DLT) within the dose-escalation safety monitoring period (D1 to D15), then escalation to the next dose level may proceed if recommended by the SMC and approved by the Sponsor. If 1 of the first 3 patients in the cohort experiences a DLT within the dose-escalation safety monitoring period (D1 to D15), the dose level may expand to a maximum of 6 patients. If no DLT occurs among the 3 additional patients enrolled at that dose level, then escalation to the next dose level may proceed if recommended by the SMC and approved by the Sponsor.

For all patients in Part A, the study will consist of a 28-day screening period, a single dose of ANK-700 administered on D1. Patients will return to the clinic on D4±1, D15, and D29±1. Additionally, patients will return to the clinic after 3 and 6 months for follow-up. Blood and plasma samples will be collected for PK and anti-drug antibody (ADA) assessments during Part A. In the event that patients are unable to return to the clinic for protocol-specified visits, alternative methods for safety assessments and data collection may be employed to ensure the safety of the patients where appropriate.

## 2.3.2 PART B: MAD (Multiple Ascending Doses)

The first MAD cohort (Cohort 4) will be initiated after the safety review of SAD Cohort 2 (Part A), a recommendation to proceed by the SMC, and approval by the Sponsor.

Patients in the MAD part will be randomized as described in Section 3.2. Patients will arrive at the clinic on the morning of dosing and will be monitored in-clinic for 24 hours after completion of their first infusion for assessment of acute safety and PK blood sample collection.

A total of 3 doses (1 dose every 3 days on D1, D4, and D7) will be administered in Part B, a regimen that was effective in animal models of MS. Patients will return to the clinic on D22, D43±2, and at 3, 6, and 12 months for follow-up.

Doses planned for evaluation in Part B include 0.3 mg/kg (Cohort 4) and 1.0 mg/kg (Cohort 5). Both Part B cohorts will employ sentinel dosing to monitor for the acute and subacute safety of multiple doses of ANK-700. In this design, the first 2 patients in each cohort (1 ANK-700 and 1 PBO) will complete all 3 doses and complete an additional 14 days of safety monitoring (through D21) before initiating dosing for any subsequent patients. Based upon the expected short half-life (< 7 minutes) of ANK-700, no accumulation is anticipated with multiple doses administered 3 days apart.

Initiation of Cohort 5 will only commence after review of the safety, tolerability, and laboratory test and available PK data of all the SAD cohorts (Cohorts 1 to 3) and Cohort 4 through D22, recommendation by the SMC, and approval by the Sponsor.

For all patients in Part B, the study will consist of a screening period of up to 28 days, followed by 3 doses of study drug, 1 dose administered on D1, D4, and D7. Blood and plasma samples will be collected for PK and ADA assessments during Part B of the study. In

the event that patients are unable to return to the clinic for protocol-specified visits, alternative methods for safety assessments and data collection may be employed to ensure the safety of the patients where appropriate.

## 2.4 Study Drug Dosage and Administration

Administration of study drug in 100 mL normal saline will be by IV infusion over approximately 30 minutes.

For Part A, patients will receive a single IV infusion of ANK-700 only (i.e. no PBO). The following doses will be given:

#### Part A (SAD)

- ANK-700 0.3 mg/kg
- ANK-700 1 mg/kg
- ANK -700 3 mg/kg

For Part B, patients will receive 3 IV infusions; each administered 3 days apart, of a given dose of either ANK-700 or PBO. Dosing groups in Part B will be as follows:

#### Part B (MAD)

- PBO
- ANK -700 0.3 mg/kg
- ANK -700 1 mg/kg

#### 3. SAMPLE SIZE, RANDOMIZATION AND BLINDING

## 3.1 Sample Size

In Part A, the number of patients enrolled into a treatment group will be based on safety and tolerability within a traditional 3+3 design. If 1 of the first 3 patients in a given cohort experiences a DLT within the dose-escalation safety monitoring period (D1 to D15), the dose level may expand to a maximum of 6 patients under this model, Part A may enroll 9 to 18 patients across 3 treatment groups, depending upon the toxicities observed. No formal hypothesis testing is planned for Part A.

Patients in Part A may be replaced if they do not receive the full dose of study drug or do not complete the D15 visit, as long as the discontinuation was not due to a DLT assessed to be related to study drug.

In Part B, the total sample size of 24 patients (n=8 ANK-700 0.3 mg/kg; n=8 ANK-700 1 mg/kg; n=8 PBO) was chosen to allow for a comparison of safety between ANK-700 and PBO, however no sample size calculation was performed.

In Part B, patients may be replaced if they do not complete all 3 doses and the D22 visit as long as they did not discontinue the study because of a related AE. No patient with a DLT will be replaced.

## 3.2 Randomization and Blinding

Once a patient has met all entry criteria, he or she will be assigned a distinct subject identifier. If a patient discontinues from the study, the subject identifier will not be reused, and the patient will not be allowed to reenter the study. Patients not eligible during the screening period, may be rescreened after 4 weeks. Patients who experience a relapse during screening may be rescreened after 28 days.

## 3.2.1 Part A (SAD) – Open Label

Part A is open-label. Patients will be assigned to receive open-label ANK-700 at a dose level based on the next available spot in the cohort(s) currently being enrolled.

## 3.2.2 Part B (MAD) – Double Blind

Part B is double-blinded, such that study personnel (eg, Investigators, site coordinators) and patients are blinded to treatment assignments and will remain blinded throughout the study. Unblinded personnel include those involved in drug preparation and allocation (eg, data systems support and pharmacists) and those involved in SMC data preparation, including the study pharmacokinetic scientist, to allow for expedited review of PK data before SMC review.

The MAD part of the study includes two cohorts, Cohort 4 (ANK-700 0.3 mg/kg) and Cohort 5 (ANK-700 1 mg/kg). In each cohort, randomization is stratified based upon a patient's use of fumarate at study entry within the interactive response technology (IRT) system.

After completion of the sentinel dosing in each cohort, the remaining patients will be randomized to ensure an overall 2:1 allocation to either ANK-700 or PBO, respectively. A total of 12 patients will be enrolled per each dose cohort (ANK-700 n = 8; PBO, n = 4).

For the sentinel dosing, the following constraints will occur for the **first randomization block** only (the first block contains the first 3 patients in each stratum):

- Within a cohort/fumarate stratum, the first 2 treatments will not be the same treatment.
- Within each cohort, Fumarate yes stratum will not be the same order of treatments as the fumarate no stratum.

The below two examples for cohort 4 show what **is not permitted** to occur in the randomization of the first blocks of Cohort 4, nor Cohort 5.

Patient Order Block Cohort Fumarate Treatment

Anokion ANK-700 Statistical Analysis Plan Final V1 07NOV2022.docx

NOT PERMITTED: The order of treatments for the fumarate yes group is the same as the fumarate no group.

Statistical Analysis Plan			ANK-700-01		6 November 2022
1	1	4	Yes	PBO	
3	1	4	Yes	ANK 0.3	
5	1	4	Yes	ANK 0.3	
2	1	4	No	PBO	
4	1	4	No	ANK 0.3	
6	1	4	No	ANK 0.3	

Or

Patient Order	Block	Cohort	Fumarate	Treatment	
2	1	4	Yes	ANK1	
3	1	4	Yes	PBO	
6	1	4	Yes	ANK1	NOT PE
1 4 5	1 1 1	4 4 4	No No No	ANK 1 ANK 1 PBO	The first treatmen same.

NOT PERMITTED: The first two treatments are the same.

After completion of each dose group in Part B, the data will be presented and reviewed by the SMC in a blinded fashion. If a medical emergency occurs, the site may be unblinded for that patient, if knowledge of the study treatment is necessary to provide appropriate urgent medical care.

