### **10.7.** ASSIGNMENT TO TREATMENT

Once a patient has met all entry criteria, he or she will be assigned a distinct patient identifier. If a patient discontinues from the study, the patient identifier will not be reused, and the patient will not be allowed to reenter the study.

In Part A, patients will be assigned to receive open-label ANK-700 at a dose level based on the next available spot in the cohort(s) currently being enrolled. Patients in Part A may be replaced if they do not receive the full dose of study drug or do not complete the D15 visit, as long as the discontinuation was not due to a DLT

In Part B, patients will be stratified based upon their use of fumarate at study entry within the IRT system. For the sentinel group, the first 2 eligible patients within each cohort will be randomized through IRT in a 1:1 ratio to receive either ANK-700 or PBO. After completion of the sentinel dosing in each cohort, the remaining 10 patients will be randomized to ensure an overall 2:1 randomization to ANK-700 and PBO. Patients in Part B may be replaced if they do not receive the full 3 doses of study drug or do not complete the D22 visit, as long as the discontinuation was not due to a DLT.

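### The first-block rules that secure the Part B sentinel pair make up to four later patients per cohort predictable, and the 8:4 split is not guaranteed as written; a separate sentinel list would avoid the predictability cheaply

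*SAP*

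**What the plan says.** Protocol 10.7 stratifies Part B by fumarate use and sets the sentinel rule at cohort level: "the first 2 eligible patients within each cohort will be randomized through IRT in a 1:1 ratio to receive either ANK-700 or PBO". The other ten patients are then randomized so that the cohort reaches 2:1 overall. Protocol 4.2 describes the sentinel pair as one patient on each treatment.

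SAP 3.2.2 implements this inside the stratified list. It defines the first block ("the first block contains the first 3 patients in each stratum") and places two rules on that block only:

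- The first rule acts inside each stratum: "Within a cohort/fumarate stratum, the first 2 treatments will not be the same treatment".
- The second rule compares the two strata and forbids identical treatment sequences in their first blocks.

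After the sentinels, "the remaining patients will be randomized to ensure an overall 2:1 allocation to either ANK-700 or PBO, respectively". The stated cohort total is 12, with 8 on ANK-700 and 4 on placebo. Both worked examples in the section show blocks of two ANK-700 and one placebo, although the text does not state that composition. Neither document gives a later block size, a cohort-level limit or balancing rule, or an expected fumarate share. Neither says who may see the first-block rules.

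**The concern.** The protocol restricts two patients per cohort. The SAP's rules act on whole blocks of three in both strata, so they reach patients enrolled after the sentinel pair, whom the protocol describes simply as randomized. Part B is double-blind, and its primary endpoint is the incidence and severity of TEAEs. Grading, relatedness and the judgement of whether an event counts as a DLT all involve discretion. If someone in the blinded team can work out an allocation, those judgements lose some of their protection. SMC review in Part B is also meant to be blinded, with the Medical Monitor and a sponsor medical representative attending as non-voting members (Protocol 4.4 and 4.8).

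A second, smaller matter is that both documents say the allocation will ensure 2:1, while stratified blocks can be left incomplete in a cohort of 12.

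**Working it through.** Write A for ANK-700 and P for placebo.

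**Inputs.** Cohort of 12 at 2:1, first block of three per stratum, and the two first-block rules (SAP 3.2.2). Sentinel pair at 1:1, then ten more (Protocol 10.7). Assumptions: first blocks contain two A and one P (from the SAP's examples); later block size and fumarate share are unstated and are varied below.

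**The plan's own figure.** 12 × 2/3 = 8 and 12 × 1/3 = 4. Equivalently, a 1:1 sentinel pair plus 7:3 among the remaining ten gives 1 + 7 = 8 and 1 + 3 = 4. The stated 8:4 is arithmetically consistent.

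**Step 1: what the rules leave.** The 2:1 orders are AAP, APA and PAA, giving 3 × 3 = 9 pairs over two strata. The first rule removes AAP, leaving 2 × 2 = 4 pairs. The second rule removes equal orders, leaving 2: (yes, no) = (APA, PAA) or (PAA, APA).

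**Step 2: consequences.**
- Position 3 is A in both surviving orders, so that patient receives ANK-700 with probability 1 instead of 2/3.
- One known assignment in position 1 or 2 of either stratum identifies which of the two pairs is in use, and so fixes both blocks.
- The two first blocks hold 6 patients, of whom 2 are the sentinels. That leaves up to 6 - 2 = 4 later patients: the two in position 3, known without any unblinding, and two more once one position-1 or position-2 assignment is known.

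**Step 3: how often all four exist.** Both strata must reach three patients. With the fumarate-yes count binomial on 12, the probability that one stratum has fewer than three is 0.56, 0.25, 0.09 and 0.04 at assumed shares of 20%, 30%, 40% and 50%.

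**Step 4: first blocks versus first six entrants.** These coincide only if the first six entrants split 3/3 by fumarate use (probability 0.08, 0.19 and 0.31 at shares of 20%, 30% and 50%). With later blocks of three, other splits leave four possible assignments (2/4 or 4/2) or six (0/6, 1/5, 5/1, 6/0).

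**Step 5: is 8:4 assured?** Assume later blocks are also of three.

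| Fumarate yes/no | P(8:4) | P(7:5) | P(9:3) |
|---|---|---|---|
| 0/12, 3/9, 6/6, 9/3, 12/0 | 1 | 0 | 0 |
| 4/8, 5/7, 7/5, 8/4 | 5/9 | 2/9 | 2/9 |
| 2/10, 10/2 | 2/3 | 1/3 | 0 |
| 1/11, 11/1 | 1/2 | 1/3 | 1/6 |

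Example, 4/8: the first blocks give 4 A and one further complete block gives 2. The incomplete yes block contributes 1 A with probability 2/3. The incomplete no block (two patients) contributes 1 A with probability 2/3 or 2 A with probability 1/3. A total of 8 needs two more A: (2/3)(2/3) + (1/3)(1/3) = 5/9.

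Weighted by binomial stratum sizes, P(8:4) is 0.718, 0.719, 0.710, 0.707 and 0.710 at shares of 20%, 30%, 40%, 50% and 60%. Both cohorts reach 8:4 with probability of about 0.71² = 0.50. If later blocks are of six, the single-cohort figure is about 0.54 to 0.67 at shares of 20-50%.

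**The case against.** The best defence is that the rules do exactly what the sentinel design requires. The strata of the first two patients are not known in advance. If both use fumarate, positions 1 and 2 of the yes block must differ. If neither does, positions 1 and 2 of the no block must differ. If they are mixed, the two first positions must differ. Of the nine pairs of 2:1 blocks of three, only the two that the SAP allows satisfy all three conditions. Nine unrestricted pairs are therefore not a fair benchmark, because most of them break the sentinel rule. This stands, and it makes the point one of method: a separate sentinel list gives the same guarantee without binding anyone else.

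The blinding risk also has limits. Using the rules requires knowing each patient's stratum and place within it, across about 15 sites. The protocol does not disclose block sizes or these rules to investigators, who grade events and assess relatedness. Nothing shows that blinded site staff hold the SAP. That one sentinel's treatment reveals the other's is inherent in Protocol 10.7.

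A reader might infer that unblinding one patient exposes five others. It does not. Unblinding a position-3 patient reveals nothing new, and unblinding a position-1 or position-2 patient newly reveals at most three, since the two position-3 treatments are already known.

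Timing matters as well. The SAP is dated November 2022, and the planned last visit is September 2023 with one-year follow-up. On the planned dates, the last randomization would fall around September 2022, so the list may already have been used.

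**Conclusion.** The point holds as a cheap improvement. If first blocks are 2:1 blocks of three, the rules leave two paired configurations, fix position 3 as ANK-700, and make up to four post-sentinel patients per cohort predictable to someone who knows the rules and the within-stratum order. The number is smaller when a stratum enrols fewer than three.

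Three stronger readings are not supported:

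- That the first six patients of a cohort follow one of two sequences. This is true only when they split 3/3 by fumarate use.
- That every third patient in a stratum is ANK-700 throughout. The rules apply to the first block only.
- That the scheme fails to deliver 8:4. It gives 8:4 with certainty for 5 of the 13 possible fumarate splits if later blocks are of three, and 8:4 is still the most likely total for the others. A limit within the IRT is neither described nor excluded. What can be said is that the split is not guaranteed as written.

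The consequence of a 7:5 or 9:3 cohort is small. No hypothesis is tested, no sample-size calculation was made, and placebo is pooled across cohorts.

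**What to change.** For any cohort not yet randomized:

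1. Allocate the first two patients of the cohort from a separate 1:1 list (one block of two), whatever their strata, as Protocol 10.7 describes.
2. Delete the two first-block rules.
3. Randomize the remaining ten from a fumarate-stratified list, with an IRT cohort limit of 7 ANK-700 and 3 placebo. Alternatively, omit the limit and describe the split as approximately 8:4.

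The cost is a revised list specification and IRT set-up. The limit has a downside: once one arm is full, the remaining allocations are determined. In simulation with stratified blocks of three (assumed), three or more allocations are determined in about 37% of cohorts, and at most five. That helps only someone who knows all earlier assignments. Before enrolment, no patient has an allocation probability of 1; the highest is about 0.85, for the last patient. Stating an approximate split avoids this at the price of an uncertain total.

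For a cohort already randomized, change nothing in the allocation. Report in the CSR the scheme used, including later block sizes and any IRT limit, the actual counts by arm and stratum, and who had access to the rules while the blind was in force.
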